7.2 Study Procedures

Provide a step by step description of all research procedures being conducted (broken down by visit, if applicable) including such information as below (where and when applicable); describe the following:

- HOW: (e.g., data collection via interviews, focus groups, forms such as surveys and questionnaires, medical/school records, audio/video/digital recordings, photographs, EKG procedures, MRI, mobile devices such as electronic tablets/cell phones, observations, collection of specimens, experimental drug/device testing, manipulation of behavior/use of deception, computer games, etc.)
- WHERE: (e.g., classrooms, labs, internet/online, places of business, medical settings, public spaces, etc.)

Subjects participating in this study will receive routine care for eating disorder at a partial hospitalization (PHP) level of care at MSHMC. In PHP, all patients have biweekly medical screening visits for the duration of their time in care, as well as weekly individual therapy sessions, individual dietician sessions, and psychiatry appointments. They have supervised meals and numerous group therapy sessions. Every three weeks, patients in PHP complete a battery of mood and eating disorder indices including those evaluated in this study; participants in this study will complete an additional two surveys with this routine battery. Participants in this study will have no alterations in their routine eating disorder care outside of study article use and these additional surveys.

Subjects will be enrolled at their first visit for eating disorder programming at child or adult partial hospitalization (PHP) programming at MSHMC adolescent medicine eating disorders clinic. Informed consent/assent will be obtained as described above.

The subject will be provided with oral naltrexone or placebo weekly from the MSHMC research pharmacy. Subjects will be given one weeks' worth of medication at a time. Subjects will be randomized at enrollment to receive either study drug (naltrexone) or placebo. Participants or parents of minor participants will be provided study drug or placebo following completion of urine drug screen and consent/assent. Patients will take the medication daily while they are in programming; after completion of programming or withdrawal from the study they will no longer be given study medication. For subjects who are enrolled in child PHP and who eat meals with parents, the families may choose to administer study drug during meals at programming. For adult patients enrolled in adult programming, subjects may choose to self-administer the medication.

On their first contact with PHP, all patients in Adult PHP complete various eating disorder indices as a part of routine care, including the ED-15, PHQ-9, GAD-7, and EDE-Q. This battery of indices is repeated every 3 weeks while a patient is in programming.

For those who are enrolled in this study, they will complete their routine indices, in addition they will also complete the BIS/BAS and the ABUSI at enrollment and at weeks 1, 3, and 6 while enrolled in the study. Participants will also be asked to take the routine indices (ED-15, EDE-Q, PHQ, GAD, BIS/BAS, and ABUSI) at week 8 or 9 for a post-treatment evaluation. These will be taken in an in-person medical appointment or electronically via RedCap

6 months after enrollment, subjects will be sent copies of ED-15, EDE-Q, PHQ, GAD, BIS/BAS, and ABUSI indices either in an in-person medical appointment or via RedCap to complete. If the patient returns for medical follow-up between 5 and 7 months after enrollment, their height, weight, and body mass index will also be recorded to determine if weight restoration was maintained.

Patients in Child PHP typically complete a different inventory every three weeks as part of routine care. If a patient choses to participate in this study they will be asked to complete the same surveys as participants in Adult PHP (ED-15, GAD-7, and PHQ-9), and they will receive the same amount and type of compensation as those who already take them as part of standard of care.

REDCap, will be used to store the surveys. Participants will be sent the link to the battery of surveys via email at the designated times listed above. The link will redirect them to the programmed surveys in REDCap. Their responses will be stored in REDCap until data is exported and stored on the secure file server (hersheymed.net/files). Only authorized study personnel will have access to the REDCap surveys and folder access on the secure network.

At initial contact with the eating disorders clinic, all patients receive an initial battery of laboratory tests as a part of the standard of care for eating disorder. These tests include liver function assays and transaminase levels. Further information about liver function test and monitoring for drug-induced liver injury is outlined in section 9.0.

7.1.1 Enrollment.

Provide a description of what procedures will be performed on visit 1 or day 1 or pre-test in order of how these will be done. If your study only involves one session or visit, use this section only and indicate 7.2.2 as not applicable.

As discussed above, patients can be enrolled at either their initial medical or initial psychiatric appointments for participation in the appropriate PHP for eating disorder.Per Joint Commission regulations of partial hospitalization programs for any psychiatric diagnosis, a complete blood count, blood chemistry, liver function test, urinalysis, and electrocardiogram must be obtained at enrollment and other studies at the program's discretion. If all necessary bloodwork, EKG, and urine studies have been obtained within the last two weeks, these results will be tracked down, recorded into the medical record, and any necessary and routine studies that have not been completed prior to this appointment will be completed at enrollment.

For patients enrolling at their medical appointment: after completion of the medical appointment, the study coordinator will approach the patient and family (if the patient is under 18 years of age), and discuss the study. The study coordinator will review the consent/assent forms, and after completion of the appointment the patient will be asked to obtain their routine studies (unless they have already been obtained as described above) within the coming seven days. A urine drug screen will be obtained at no cost to the participant and its results will not be placed into the medical record. Patients screening positive for any opioid will be excluded from the study and offered referral for addiction counseling. For potential female subjects, a serum pregnancy test will also be obtained at this time. Patients screening positive for pregnancy will be referred for options counseling

For patients enrolling at their psychiatric appointment: Joint Commission regulations regarding obtaining lab studies are unchanged, regardless of initial appointment location. All patients in PHP have biweekly medical appointments as a part of routine care, and routine enrollment labs are typically

obtained at the first medical appointment after first psychiatric appointment during the first seven days of programming. Labs will be ordered at that appointment and obtained within seven days, or entered into the medical record if obtained elsewhere, at that time. A urine drug screen will be obtained at no cost to the participant and its results will not be placed into the medical record. Patients screening positive for any opioid will be excluded from the study and offered referral for addiction counseling. For potential subjects who are female, a serum pregnancy test will also be obtained at this time. Patients with a positive pregnancy test will be referred for options counseling.

All participants, regardless of sex assigned at birth, gender, or menarchal status, will be required to use a highly reliable form of contraception should they be sexually active. Acceptable options have failure rates of less than 1% and include: combined hormonal contraceptives (such as oral contraceptive pills, patch, or vaginal ring), intrauterine device, depot-medroxyprogesterone injection, etonogesterel-containing implants, and progestin-only contraceptive pills. Condoms, either internal or external, are not sufficient contraception if used alone. If a participant with a birth-assigned sex of female discloses coitus while participating in the study either without the use of contraception or with contraceptive failure (such as a broken condom with no second method of contraception), the participant will be offered a prescription for emergency contraceptive (ulipristal acetate or levonorgesterel 1.5mg) within 72 hours after coitus, pregnancy testing 14 days after the episode of coitus with referral according to results, and will be withdrawn from the study.

7.1.2 Visit 2 or Day 2 or Post-test, etc. (If applicable)

Provide a description of what procedures will be performed on visit 2 or day 2 or post-test in order of how these will be done. If your study involves more than two sessions or visits replicate this section for each additional session or visit (e.g., 7.2.3, 7.2.4, etc.).

On the first day of study participation after enrollment, all subjects will receive a complete set of vital signs (including heart rate, blood pressure, respiratory rate, temperature, and weight) and urine drug screen including screening for opioid substances prior to receipt of their first dose of study article.

Routine care during PHP for any participant includes every-other-week in-person medical exams for the duration of the patient's stay in program, as well as frequent appointments following completion of PHP, until discharge from clinic. At each medical appointment, patients receive a comprehensive physical exam including complete vital signs as above, and are routinely asked about mood changes, physical changes, difficulty or ease of adhering to routine program protocols, etc. All patients participating in PHP complete routine surveys to assess eating disorder recovery at intake and every three weeks until completion of program. For participants in this study, the documentation of their three- and six-week appointments will be reviewed for evidence of adverse effects related to study participation by study personnel. Participants will also complete two additional surveys, the ABUSI and BIS/BAS, beyond their routine PHP surveys at weeks three, six, and eight/nine. Routine medical testing will be obtained according to clinical need at all medical visits, regardless of participation in this study, for all patients participating in PHP.

For patients participating in this study, liver function panel will be obtained once every 3 weeks at no cost to study participants for the purpose of monitoring drug safety, as well as completion of all of the relevant study indices

The vast majority of patients who require PHP have a routine medical follow-up at approximately six months; for those who do not this appointment will be made at no cost to the participant. At this appointment, participants will again undergo a comprehensive physical

exam, receive a complete set of vital signs, be interviewed on eating disorder symptomatology, and be asked to fill out study indices again and will be given a \$25 Greenphire Clincard card for their time.

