7.1 Study Design

Describe and explain the study design.

This is a double-blind, randomized, placebo-controlled study. We have developed the following schedule of events. All events with a superscript $^{\circ}$ are for study purposes only and are not part of the standard of care:

	Pre-Enrollment Screening: Medical	Enrollment	Week 1	Week 2	Week 3	Week 4	Week 5	Week 6 (end of treatment	Week 8-9 (post- treatment)	Six Months
Intervention								_	>	
Initial Medical Assessment	Х									
Subsequent Medical Assessment, including comprehensive review of systems			x		x		x		х	х
Initial Psychiatry Assessment	X									
Subsequent Psychiatric Assessment, including suicidal ideation			х	х	х	х	х	х	х	х
Discussion of risks and benefits, inclusion and exclusion criteria ^o		х								
Consent/Assent ^o		Х								
\$25 Greenphire Clincardo		Х								х
Urine Drug Screen ^o		Х								
Serum Pregnancy Test (female participants)°		х								
Urine Pregnancy Test (female participants)°					х			х		
Administer Study Article ^o			Х	Х	х	Х	Х	х		
EKG	X									
AST	X				Xº			Xº		
ALT	Х				χ°			Xo		
Total Bilirubin	Х				Xº			Xº		
Direct bilirubin	Х				Xº			Xº		
Heart Rate	Х		Х	Х	Х	Х	Х	Х	Х	Х
BMI	X		Х	Х	Х	Х	Х	X	Х	Х
Height	X		Х	X	X	X	Х	X	X	Х
Weight	X		X	X	X	X	X	X	X	X
Blood Pressure	X		X	X	X	X	X	X	X	X
Temperature Adverse event monitoring ^o	Х		X	x	x	x	x	x	X	X
Suicidal Ideation Screening (ASQ			^	^	^	^	^			
for age <17or C-SSRS for age 18+)		х	Х	Х	х	Х	Х	х	Х	Х
ED-15		Х	х		х			Х	X	х
EDE-Q		Х	х		х			Х	X	Х
ABUSI°		Х	Х		х			Х	Х	Х
GAD-7		Х	х		х			Х	Х	Х
PHQ-9		Х	Х		Х			Х	X	Х
BIS/BAS°		Х	Х		Х			Х	Х	Х

Note: Medical assessments may occur in weeks 1,3 etc or 2,4 etc depending on standard of care for that patient. As long as patients are seen within a 14 day interval (2 week timeframe), the exact week intervals (1,3 or 2,4) may vary. Additionally, the 6 month follow up appointment may take place any time between 5-7 months after study enrollment ends.

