7.2 Duration of Participation

Describe how long subjects will be involved in this research study. Include the number of sessions and the duration of each session - consider the total number of minutes, hours, days, months, years, etc.

Subjects will be enrolled in this study for a total of six months, starting at enrollment in PHP, and continuing to their final 6-month follow-up visit. They will have study interventions at 0, 3, and 6 weeks, and again at six months. They will take study medication while in PHP, and stop once six weeks of study duration is completed. Duration of PHP is individualized, but is on average about 8 weeks. Duration of PHP will not be dependent upon study participation.

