9.3 Method of collection of safety information

Describe the method by which the safety information will be collected (e.g., with case report forms, at study visits, by telephone calls and with subjects).

All patients participating in PHP receive biweekly medical visits, including comprehensive physical exam, vital signs, review of suicidal thoughts or behaviors, review of systems, and review of eating disorder symptom severity and frequency as a part of routine care in PHP. Patients also fill out the Columbia Suicide Severity Rating Scale (C-SSRS a metric assessing for the presence and severity of suicidality) or Ask Suicide Screening Questions (ASQ, a similar metric) once weekly while in care, with patients age 18 and older using the C-SSRS and patients age 13-17 using the ASQ. Participants in this study will be no different, with the notable exception of every-three-week liver function and urine pregnancy tests (assigned female at birth patients only).

Study participants' charts will be reviewed weekly while they are in program by the PI and the study coordinator for any of the above-mentioned possible new diagnoses, lab results, C-SSRS results, as well as review of all routine care detailed above. Study staff who provide direct care to participants will alert the PI and the study coordinator of any adverse events encountered during the course of routine care. The results of all safety screenings will be kept in a comprehensive, secure database and will be reviewed weekly by the study team

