19.1.2 Safety Monitoring

Include this section if FDA regulations apply to this study (see "WORKSHEET: Drugs (HRP-306)" and "WORKSHEET: Devices (HRP-307)". HRP-306 and HRP-307 can be accessed by clicking the Library link in CATS IRB (http://irb.psu.edu).

Indicate the process for identifying, recording and reporting adverse events.

Specify roles for adverse event recording and monitoring. Indicate each staff member's role in the adverse event reporting process. Include the following if applicable:

The **Principal Investigator** will confirm that all adverse events (AE) are correctly entered into the AE case report forms by the coordinator; be available to answer any questions that the coordinators may have concerning AEs; and will notify the IRB, FDA, sponsor and/or DSMB of all applicable AEs as appropriate. All assessments of AEs will be made by a licensed medical professional who is an investigator on the research.

The **Research Coordinator** will complete the appropriate report form and logs; assist the PI to prepare reports and notify the IRB, FDA and/or DSMB of all Unanticipated Problems/SAE's.

The **Monitor** will confirm that the AEs are correctly entered into the case report forms. The Monitor will also confirm that the adverse events are consistent with the source documents and are reported to the appropriate regulatory bodies as required.

The principal investigator assumes final responsibility for monitoring the safety of this study. Monitoring for adverse effects to medication will occur at all biweekly medical appointments as a part of routine care during PHP. If a participant develops any observable harm that is probably related to the study articles or materials the participant will be withdrawn from the study and adverse event reporting per IRB protocol will be performed.

The Principal Investigator will confirm that all adverse events (AE) are correctly entered into the AE case report forms by the coordinator; be available to answer any questions that the coordinators may have concerning AEs; and will notify the IRB, FDA, sponsor and/or DSMB of all applicable AEs as appropriate. All assessments of AEs will be made by a licensed medical professional who is an investigator on the research.

The Research Coordinator will complete the appropriate report form and logs; assist the PI to prepare reports and notify the IRB, FDA of all Unanticipated Problems/SAE's.

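### Adverse-event review is described in several unreconciled ways, and no rule clearly covers participants who leave PHP before week 6 but stay on study article

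*Combined protocol and SAP*

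**What the plan says.** Rules for reviewing adverse effects:

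- Section 7.1.2, for study participants: "the documentation of their three- and six-week appointments will be reviewed for evidence of adverse effects related to study participation by study personnel". The type of appointment is not stated. The same paragraph describes the medical calendar: "Routine care during PHP for any participant includes every-other-week in-person medical exams for the duration of the patient's stay in program".
- Section 9.3: "Study participants' charts will be reviewed weekly while they are in program by the PI and the study coordinator". Study staff giving direct care also alert the PI to adverse events.
- Sections 9.1, 9.5 and 9.6: the PI and coordinator or study team review safety data weekly, with no mention of PHP status. Section 9.4 has safety data obtained weekly.
- Section 19.1.2, repeated in 19.1.1: "Monitoring for adverse effects to medication will occur at all biweekly medical appointments as a part of routine care during PHP".
- Section 18.2: participants are asked about adverse events at study visits and in routine PHP care.

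What happens after PHP:

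- Section 7.3.2 carries study article to six weeks in total. Its example is three weeks in PHP followed by three weeks after discharge.
- Section 7.2 (Study Procedures) says study medication is no longer given once programming is complete. Section 9.2 says participants are then no longer obliged to take it, and no longer requires weekly psychiatric evaluation, laboratory evaluation or suicide assessment.
- Section 19.1.1 has the week-6 measures emailed to anyone who has finished PHP.

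**The concern.** Staff following 7.1.2, 9.3 or 19.1.2 would be working to three different instructions, with no statement of which governs. The mismatch matters most where the rules stop together, which is after discharge with study article continuing. An adverse event in that period could go unrecorded because no section clearly says who asks about it, when, or what documentation is reviewed.

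Adverse events feed the withdrawal rule in 19.1.2 and the suspension triggers in 9.8, including the open-ended one for any serious condition possibly related to study article. There is also a comparison problem. Section 9.2 anticipates that participants doing well on study article may have a shorter stay. If so, more of the naltrexone arm would move into the period with least ascertainment, and adverse-event counts would not be like for like between arms.

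**Working it through.** The plan has no figure of its own to reproduce here. The check sets the passages against each other and counts weeks.

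**1. Do weeks 3 and 6 fit the medical calendar?** The note under the schedule in 7.1 says "Medical assessments may occur in weeks 1,3 etc or 2,4 etc depending on standard of care for that patient". The strict patterns are {1, 3, 5} and {2, 4, 6}:

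- {1, 3, 5} ∩ {3, 6} = {3}
- {2, 4, 6} ∩ {3, 6} = {6}

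Weeks 3 and 6 are 6 − 3 = 3 weeks apart, an odd number, so strict alternate-week visits cannot include both. But the note adds: "As long as patients are seen within a 14 day interval (2 week timeframe), the exact week intervals (1,3 or 2,4) may vary". Listing every pattern over weeks 1-6 with gaps of at most two weeks, a first visit by week 2 and a last visit at week 5 or later (the last two limits are assumptions) gives 21 patterns. Nine contain both weeks, for example 1-3-5-6, and each of the nine needs at least four visits.

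**2. Are there other appointments in weeks 3 and 6?** Yes, during PHP. Section 7.2 (Study Procedures) lists biweekly medical visits "as well as weekly individual therapy sessions, individual dietician sessions, and psychiatry appointments", and the schedule ticks psychiatric assessment in each of weeks 1-6. These weeks are also study time points. Section 7.2 (Duration of Participation) says: "They will have study interventions at 0, 3, and 6 weeks, and again at six months".

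**3. Nominal occasions in six treatment weeks.** 7.1.2: 2. Biweekly visits under 19.1.1 and 19.1.2: 6 / 2 = 3. Weekly review under 9.1, 9.3, 9.5 and 9.6: 6. The biweekly rule concerns monitoring at the visit and the others later review, so these are not exact substitutes.

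**4. After early discharge.** Let d be the last week in PHP, assuming study article starts with PHP. Under 7.3.2, weeks on study article outside PHP = 6 − d. Section 9.2 provides at least one medical follow-up two weeks after program, at about week d + 2.

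| d | Weeks on study article outside PHP | Assured medical follow-up |
|---|---|---|
| 1 | 5 | week 3 |
| 2 | 4 | week 4 |
| 3 | 3 | week 5 |
| 4 | 2 | week 6 |
| 5 | 1 | week 7, after last dose |

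For the protocol's own example (d = 3), half of the treatment period (3 / 6) lies outside PHP. The assured follow-up is near week 5, which 7.1.2 does not name. Only d = 1 and d = 4 put it in a week that 7.1.2 names.

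**5. Which rules still operate in those weeks?**

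- 9.3: ended, because it applies in program only.
- 19.1.1 and 19.1.2: ended, because they apply to PHP visits.
- 9.1, 9.4, 9.5 and 9.6: no PHP limit, but 9.2 has withdrawn the requirement for weekly evaluations that would supply much of the data.
- 18.2: applies at study visits, but the week-6 contact may be an emailed survey.
- 7.1.2: applies if a week-6 appointment takes place.
- Schedule, adverse event row: appears to continue, but in the text available it is run together with its neighbour and cannot be relied on either way.

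**The case against.** The best defence is that Section 9 is the safety monitoring plan and sets weekly review. Section 7.1.2 does not say that only the week 3 and 6 documentation is reviewed, so it reads naturally as an added check at the study time points. Sections 9.1, 9.5 and 9.6 carry no PHP limit, treating staff report events to the PI, 7.1.2 mentions frequent appointments after PHP, and 14.1 expects travel for a six-week follow-up. All of this stands for time in PHP: under the weekly rule, documentation there is reviewed.

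A reader might go further and infer that no participant can have both reviewed appointments, or that only one of three medical visits, and so about a third of treatment time, is ever examined. The documents do not support that. Section 7.1.2 says neither medical nor only, psychiatry appointments are weekly in PHP, the medical weeks may shift within 14 days, and the weekly reviews run alongside.

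The defence does not close the period after discharge. A weekly review with no stated source of data is not a collection rule, and the follow-up in 9.2 need not fall while the participant is still on study article.

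**Conclusion.** The point holds as an inconsistency in the safety wording with one substantive gap. During PHP the weekly review is adequate, and the 7.1.2 sentence needs only a definition. For participants who leave PHP before week 6 and continue study article, between one and five treatment weeks (three in the protocol's example) have no clearly defined adverse-event collection or chart review.

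This rests on 7.3.2 being followed. If study article in fact stops at discharge, as 7.2 (Study Procedures) reads, the on-treatment gap largely disappears, so that contradiction has to be settled as well. The number affected cannot be computed. The documents give only an average stay of about 8 weeks, which suggests early leavers are a minority without showing it. Safety is not a listed endpoint in Section 1, so the consequence is for participant protection and the completeness of adverse-event reporting rather than for the primary analysis.

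**What to change.** State one rule, in the same words, in 7.1.2, 9.3, 9.4, 19.1.1 and 19.1.2: adverse events are collected, and all available documentation is reviewed, weekly from first to last dose of study article whether or not the participant is still in PHP, and again at the scheduled week 8-9 contact. Name the source of information after discharge. The weekly capsule hand-over in 7.3.4 and 7.3.6.1 is one existing contact to which adverse-event questions could be attached, if it continues for those who have left.

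In 7.1.2, define which appointments are meant and say that the check adds to the weekly review.

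Reconcile 7.2 (Study Procedures) and 9.2 with 7.3.2 on whether study article continues after PHP. Which is intended is for the investigators to decide; the review rule above works under either.

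The cost is wording in five sections plus that reconciliation. Weekly review is already planned, so the added work is a small amount of contact and chart review for early leavers.
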